		4.1 Design 6.1 Study Intervention(s) Administered
		6.3 Assignment to Study Intervention
		9.1 Statistical Hypotheses
		9.1.2 Multiplicity Adjustment
		9.3.2 Primary Endpoints/Estimands Analysis
		9.5.1 Immunogenicity
	Nonsubstantial Modification(s)	
Adjusted the wording to allow for greater flexibility in evaluating participants, encompassing symptoms beyond the 3 previously specified symptoms.	The updated wording will allow greater flexibility in evaluating participants in timely manner.	8.10.6 Additional Procedures for Monitoring of Potential Myocarditis or Pericarditis
As reflected in PACL 3.0 (29 Jan 2024), the protocol has been updated to include myocarditis and pericarditis wording.	The text has been updated to align with the text used in the standalone BNT162b2 XBB.1.5 wording (which was updated).	8.10.6 Additional Procedures for Monitoring of Potential Myocarditis or Pericarditis

Description of Change	Brief Rationale	Section # and Name
As reflected in PACL 3.0 (29 Jan 2024), the protocol has been updated to reflect changes to the contact procedure for urgent medical questions directed to the sponsor.	The process for contacting a medically qualified individual has changed from a medical escalation process via a Pfizer Call Center to direct clinical team contact using a Study Team Contact List.	10.1.12 Sponsor's Medically Qualified Individual
As reflected in PACL 3.0 (29 Jan 2024), the protocol has been updated to reflect the retirement of the Emergency Contact Card.	The Emergency Contact Card is being replaced by a study information card and will no longer be referenced.	10.1.12 Sponsor's Medically Qualified Individual
Added minor clarification related to left deltoid reactogenicity and confirm compliance with thermometer instructions.	To further clarify that left deltoid reactogenicity should be considered an AE.	8.3.4.2 Local Reactions 8.3.4.4 Fever 8.4.1 Time Period and Frequency for Collecting AE and SAE Information 8.10.5 Unscheduled Visit for a Grade 3 or Suspected Grade 4 Reaction
Updated the primary estimands for Cohort 2.	Updated the primary estimands for Cohort 2 for clarity.	1.1 Synopsis 3 Objectives, Endpoints, and Estimands 9.3.2 Primary Endpoints/Estimands Analysis
Added a secondary immunogenicity objective for Cohort 2.	The addition of this secondary immunogenicity objective will allow demonstration of the superiority of HAI immune responses.	1.1 Synopsis 3 Objectives, Endpoints, and Estimands 9.1 Statistical Hypotheses

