#### 4. STUDY DESIGN

#### 4.1. Design

This is a Phase 3 observer-blinded study to evaluate the safety, tolerability, and immunogenicity of selected when administered in combination with BNT162b2 (Omi XBB.1.5) compared to a licensed inactivated QIV administered in the deltoid opposite to that used for administration of BNT162b2 (Omi XBB.1.5) in healthy adults 18 through 64 years of age. Additionally, the study will evaluate administered in combination with BNT162b2 (Omi XBB.1.5) in comparison to standalone administration of QIV, CCI or BNT162b2 (Omi XBB.1.5). The vaccine candidates are divided into cohorts, which will be studied in a staggered manner, as required by the clinical plan. This study will be observer-blinded (sponsor-blinded), where up to approximately 8550 total participants 18 through 64 years of age will be enrolled into 1 of 3 cohorts:

Cohort 1: Approximately 450 participants enrolled and randomized in a 2:1 ratio by site-based randomization to 1 of the following:

- Arm A: CC BNT162b2 (Omi XBB.1.5) administered in the right deltoid and placebo administered in the left deltoid, concurrently.
- Arm B: 30 μg BNT162b2 (Omi XBB.1.5) administered in the right deltoid and licensed QIV

Enrollment of Cohort 1 will be paused in the IRT after the randomization of approximately 450 participants into Cohort 1. Safety data (including e-diary reactogenicity data, SAEs, AEs, and AESIs) of approximately 450 vaccinated participants will be evaluated by the EDMC after 60 days

Cohort 2: Approximately 4500 participants enrolled and randomized in a 2:1 ratio by site-based randomization to 1 of the following:

- Arm C: CCI BNT162b2 (Omi XBB.1.5) administered in the right deltoid and placebo administered in the left deltoid, concurrently.
- Arm D: 30 μg BNT162b2 (Omi XBB.1.5) administered in the right deltoid and licensed QIV (CCI) administered in the left deltoid, concurrently.

Cohort 3: Approximately 3600 participants 18 through 64 years of age will be enrolled and randomized in a 2:2:1:1 ratio by site-based randomization to 1 of the following:

- Arm E: CCI /BNT162b2 (Omi XBB.1.5) administered in the right deltoid.
- Arm F: 30 μg BNT162b2 (Omi XBB.1.5) administered in the right deltoid.
- Arm G: licensed QIV (CCI) administered in the right deltoid.
- Arm H: deltoid.

See Section 6.1.1 for additional details on study intervention administration in all cohorts.

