#### 8.3.4. Electronic Diary

All participants will be required to complete a reactogenicity e-diary after vaccination given at Visit 1, through an application installed on a provisioned device or on the participant's own personal device. All participants will be asked to monitor and record local reactions,

systemic events, and use of antipyretic medication for 7 days, or longer for ongoing symptoms, from the day of administration of the study intervention given at Visit 1. The reactogenicity e-diary allows recording of these assessments each day, thus providing the accurate representation of the participant's experience. Data on local reactions and systemic events reported in the reactogenicity e-diary will be transferred electronically to a third-party vendor, where they will be available for review by investigators and the Pfizer clinicians at all times via an internet-based portal.

At intervals agreed to by the vendor and Pfizer, these data will be transferred electronically into Pfizer's database for analysis and reporting. Generally, these data do not need to be reported by the investigator in the CRF as AEs. However, if a participant withdraws because of events reported in the e-diary, the event(s) should be recorded on the CRF, regardless of whether the investigator considers the event(s) to be clinically significant. If a participant missed reporting an event in the e-diary and reports it to the study site instead, the event should also be recorded on the CRF.

Investigators (or designee) will be required to review the reactogenicity e-diary data online at frequent intervals to evaluate participant compliance and as part of the ongoing safety review.

The investigator or designee must obtain stop dates from the participant for any symptoms ongoing on the last day from Day 7 onwards until resolution. The stop dates should be documented in the source documents and the information entered in the CRF.

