#### 8.3.4.2. Local Reactions

During the reactogenicity e-diary reporting period, participants will be asked to assess redness, swelling, and pain at the injection site and to record the symptoms in the reactogenicity e-diary. Local reactions will be assessed at the injection site on the right deltoid only after vaccinations given at Visit 1.

Note: Any local reaction occurring at the injection site on the left deltoid will be collected in the CRF as an AE.

If a local reaction persists beyond the end of the 7-day e-diary collection period following vaccination, the participant will be requested to report that information and/or any new reactogenicity reactions that develop to the investigator or the study staff. The investigator will enter this additional information in the CRF.

Participants will be provided with a measuring device. Redness and swelling will be measured and recorded in measuring device units (range: 1 to 21) and then categorized

during analysis as absent, mild, moderate, or severe based on the grading scale in Table 3. Measuring device units can be converted to centimeters according to the following formula: 1 measuring device unit = 0.5 cm. Pain at the injection site will be assessed by the participant as absent, mild, moderate, or severe according to the grading scale in Table 3.

If a Grade 3 local reaction is reported in the reactogenicity e-diary, a telephone contact should occur to ascertain further details and determine whether a site visit is clinically indicated. Only an investigator or medically qualified person is able to classify a participant's local reaction as Grade 4. If a participant experiences a confirmed Grade 4 local reaction, the investigator must immediately notify the sponsor.

Table 3.	Local Reaction	Grading Scale
----------	----------------	---------------

	Mild (Grade 1)	Moderate (Grade 2)	Severe (Grade 3)	Potentially Life-Threatening (Grade 4)
Pain at the injection site	Does not interfere with activity	Interferes with activity	Prevents daily activity	Emergency room visit or hospitalization for severe pain
Redness	>2.0 cm to 5.0 cm (5 to 10 measuring device units)	>5.0 cm to 10.0 cm (11 to 20 measuring device units)	>10 cm (≥21 measuring device units)	Necrosis or exfoliative dermatitis
Swelling	>2.0 cm to 5.0 cm (5 to 10 measuring device units)	>5.0 cm to 10.0 cm (11 to 20 measuring device units)	>10 cm (≥21 measuring device units)	Necrosis

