#### Additionally:

- Any AE occurring up to 48 hours after any subsequent blood draws and deemed related to study procedures must be recorded in the CRF.
- Any local reactogenicity event that occurs in the left deltoid is to be reported as an AE in the CRF.

SAEs will be collected from the time the participant provides informed consent through and including Visit 3. Deaths, pneumonia, and hospitalizations will be recorded for the entire study duration, as AEs/SAEs as appropriate.

Follow-up by the investigator continues throughout the active collection period and until the AE or SAE or its sequelae resolve or stabilize at a level acceptable to the investigator.

When a clinically important AE remains ongoing at the end of the active collection period, follow-up by the investigator continues until the AE or SAE or its sequelae resolve or stabilize at a level acceptable to the investigator and Pfizer concurs with that assessment.

For participants who are screen failures, the active collection period ends when screen failure status is determined.

If the participant withdraws from the study and also withdraws consent for the collection of future information, the active collection period ends when consent is withdrawn.

If a participant permanently discontinues or temporarily discontinues from the study because of an AE or SAE, the AE or SAE must be recorded on the CRF and the SAE reported using the Vaccine SAE Report Form or via PSSA.

Investigators are not obligated to actively seek information on AEs or SAEs after the participant has concluded study participation. However, if the investigator learns of any SAE, including a death, at any time after a participant has concluded study participation, and they consider the event to be reasonably related to the study intervention, the investigator must promptly report the SAE to Pfizer using the Vaccine SAE Report Form or via PSSA.

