- Unblinded site staff member(s) will dispense/administer 1 dose of study intervention into the deltoid muscle of the appropriate arm as detailed in Section 6.1.1. Please refer to the IPM for further instruction on this process.
- Blinded site staff must observe the participant for at least 30 minutes after study intervention administration for any acute reactions. Record any acute reactions (including time of onset) in the participant's source documents, on the AE CRF, and on an SAE form as applicable.
- Explain the e-diary technologies available for this study (see Section 8.3.4), and assist the
  participant in downloading the study application onto the participant's own device or
  issue a provisioned device if required.
- Provide instructions on reactogenicity e-diary completion and ask the participant to complete the reactogenicity e-diary from Day 1 through Day 7 or longer until any symptoms that are ongoing are resolved, with Day 1 being the day of vaccination.
- Issue a measuring device to measure local reactions at the right arm injection site and a thermometer for recording daily temperatures; provide instructions on their use.
- Ask the participant to contact the site staff or investigator immediately if the participant experiences any of the following from Day 1 through Day 7 after vaccination (where Day 1 is the day of vaccination) to determine if an unscheduled reactogenicity visit is required:
  - Fever ≥39.0°C (≥102.1°F).
  - Redness or swelling at the right arm injection site measuring greater than 10 cm (>20 measuring device units).
  - Severe pain at the right arm injection site.
  - Any severe systemic event.
- Record AEs, SAEs, and AESIs as described in Section 8.4.
  - Remind participants to inform the study staff of any AEs and SAEs that occur for the duration of the trial as described in Section 8.4
- Ask the participant to contact the site staff or investigator if a medically attended event (eg, doctor's visit, emergency room visit) or hospitalization occurs.
- Ask the participant to contact the site staff or investigator if the participant experiences
  acute chest pain, shortness of breath, or palpitations (see Section 8.10.6).
- Schedule an appointment for the participant to return for the next study visit.

- Remind the participant to bring the e-diary to the next visit.
- Complete the source documents.

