#### 8.10.5. Unscheduled Visit for a Grade 3 or Suspected Grade 4 Reaction

If a Grade 3 local reaction in the right arm (Section 8.3.4.2), systemic event (Section 8.3.4.3), or fever (Section 8.3.4.4) is reported in the reactogenicity e-diary, a telephone contact should occur to ascertain further details and determine whether a site visit is clinically indicated. If a suspected Grade 4 local reaction in the right arm (Section 8.3.4.2), systemic event (Section 8.3.4.3), or fever (Section 8.3.4.4) is reported in the reactogenicity e-diary, a telephone contact or site visit should occur to confirm whether the event meets Grade 4 criteria.

A site visit must be scheduled as soon as possible to assess the participant unless any of the following is true:

- The participant is unable to attend the unscheduled visit.
- The local reaction/systemic event is no longer present at the time of the telephone contact.
- The participant recorded an incorrect value in the reactogenicity e-diary (confirmation of a reactogenicity e-diary data entry error).
- The PI or authorized designee determined it was not needed.

This telephone contact will be recorded in the participant's source documentation and the CRF.

If the participant is unable to attend the unscheduled visit, or the PI or authorized designee determined it was not needed, any ongoing local reactions/systemic events must be assessed at the next study visit.

During the unscheduled visit, the reactions should be assessed by the investigator or a medically qualified member of the study staff, such as a study physician or a study nurse, as applicable to the investigator's local practice, who will:

- Measure oral temperature (°F/°C).
- Measure minimum and maximum diameters of redness in the right arm (if present).
- Measure minimum and maximum diameters of swelling in the right arm (if present).
- Assess injection site pain in the right arm (if present) in accordance with the grades provided in Section 8.3.4.2.
- Assess systemic events (if present) in accordance with the grades provided in Section 8.3.4.3.
- Assess for other findings associated with the reaction and record these on the CRF if appropriate.

The investigator or an authorized designee will complete the unscheduled visit assessment page of the CRF.

Note: Any left arm reactogenicity event should be collected in the CRF on the AE log page.

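### In Cohorts 1 and 2, local reactions at the QIV site count as AEs while those at the combination's site go mainly to the e-diary tables, and the visible SAP lists no AE summary by arm that sets injection-site reactions aside

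*Protocol*

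**What the plan says.** **Left deltoid.** Protocol 8.3.4.2 has the rule "Any local reaction occurring at the injection site on the left deltoid will be collected in the CRF as an AE". Section 8.4.1 repeats it: "Any local reactogenicity event that occurs in the left deltoid is to be reported as an AE in the CRF". Section 8.10.5 adds "Any left arm reactogenicity event should be collected in the CRF on the AE log page". The rule is deliberate: the Amendment 2 summary of changes gives its purpose as "To further clarify that left deltoid reactogenicity should be considered an AE".

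**Right deltoid.** Local reactions on this side are solicited in the e-diary, and Protocol 8.3.4 says of e-diary data: "Generally, these data do not need to be reported by the investigator in the CRF as AEs". SAP 3.1.1 limits the local-reaction endpoint to this side. There are exceptions:
- Reactions seen in the observation period after injection fall under 8.10.1: "Record any acute reactions (including time of onset) in the participant's source documents, on the AE CRF".
- Events that lead to withdrawal, and events missed in the diary but told to the site, are entered on the CRF (8.3.4).
- A reaction lasting past Day 7 is also entered on the CRF (8.3.4.2, the sentence beginning "If a local reaction persists beyond the end of the 7-day e-diary collection period following vaccination"). Its AE status is not stated.

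**What each arm receives.** In Arms A and C the combination is "administered in the right deltoid and placebo administered in the left deltoid, concurrently" (Protocol 4.1). In Arms B and D, BNT162b2 goes in the right deltoid and QIV in the left (4.1 and Table 1).

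**AE analysis.** SAP 6.1.1.2.1 tabulates participants with any AE, and by SOC and PT, for each vaccine group. Between-arm differences with intervals are planned for Tier 2 terms, and for Tier 1 terms if any are named later. SAP 6.1.1.2.2 adds related AEs, severe AEs, AEs of special interest, immediate AEs and listings. None of these leaves out injection-site reactions.

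**The concern.** One rule applies to all arms, but the products in the left arm differ. The influenza component is injected on the right in Arms A and C and on the left in Arms B and D, so its local reactions fall mainly in different tables. The right-deltoid reactogenicity table omits QIV-site reactions by its stated scope, and the AE table includes them.

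A reader who sets Arm C beside Arm D on any AE, related AEs (where investigators judge the reactions related) or severe AEs is then not comparing like with like. Part of any gap may reflect only where the influenza vaccine was injected. AEs through 4 weeks is a primary safety endpoint, and Protocol 9.5.1 sizes the study partly to give a safety database for licensure, so these rows will be read side by side even without a formal test.

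**Working it through.** **Inputs from the documents.** Cohort 2 has about 4500 participants randomized 2:1: 4500 × 2/3 = 3000 in Arm C and 4500 × 1/3 = 1500 in Arm D. A PT is Tier 2 if at least 1% of an arm reports it (SAP 5.2.1), which is 15 of 1500 in Arm D. The plan prints no figure on this point to reproduce.

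**Assumptions.** The documents give no background AE rate and no left-arm rate. I let the rate b of all other AEs be 5% to 12%, equal in both arms, and let s be the rate of left-deltoid reactions reported as AEs.

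**Any-AE row under independence.** Rate = 1 − (1 − b)(1 − s), so C minus D = −(1 − b)(s_D − s_C).

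| s in D / s in C | b = 5% | b = 8% | b = 12% |
|---|---|---|---|
| 1% / 1% | 0 | 0 | 0 |
| 2% / 1% | -0.95 | -0.92 | -0.88 |
| 5% / 2% | -2.85 | -2.76 | -2.64 |
| 10% / 3% | -6.65 | -6.44 | -6.16 |
| 1% / 2% | +0.95 | +0.92 | +0.88 |

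Entries are percentage points.

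**Overlap.** Take b = 8% and the pairs 2/1, 5/2 and 10/3. If left-arm reporters have no other AE, the difference is s_C − s_D: -1.0, -3.0 and -7.0. If they overlap fully with other AE reporters, it is max(b, s_C) − max(b, s_D): 0, 0 and 8 − 10 = -2.0.

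**As the SAP would print it.** The planned any-AE output is one Clopper-Pearson interval per arm. With b = 8% and 5% / 2%, Arm C is 295/3000 = 9.8% (8.8 to 11.0) and Arm D is 189/1500 = 12.6% (11.0 to 14.4).

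**What the PT rows recover.** If every report codes to one PT, the Miettinen-Nurminen differences for the three pairs are -1.0 (-1.9 to -0.3), -3.0 (-4.3 to -1.9) and -7.0 (-8.7 to -5.4). With an even, non-overlapping split over pain, redness and swelling:
- 2% in D is 30/1500, or 10/1500 = 0.67% per PT, so there is no Tier 2 row. The total in D must reach 3 × 15 = 45/1500 = 3%.
- 5% / 2% gives 20/3000 against 25/1500 per PT: -1.0 (-1.8 to -0.4).
- 10% / 3% gives 30/3000 against 50/1500 per PT: -2.3 (-3.4 to -1.4).

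**What they cannot recover.** Suppose a reader knows the any-AE rate A and the share L with an injection-site AE. The rate without those events is only known to lie between A − L and A. In the 8%, 5% / 2% case that is 9.84 − 2 = 7.84% to 9.84% in C, and 12.6 − 5 = 7.6% to 12.6% in D. The difference could then be anything from 7.84 − 12.6 = -4.76 to 9.84 − 7.6 = +2.24 points, although the other-AE rates were set equal.

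**The case against.** The strongest reply is that nothing here is wrong. The safety objective is to describe, the rule is the same in every arm, and QIV-site reactions are real events of the Arm B and D regimens. A reader might infer that the any-AE estimate is biased or that the plan contains an error. The documents do not support that: the all-inclusive row correctly estimates the endpoint as defined. This part of the objection stands in full.

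It also stands that a C-minus-D any-AE difference is not a planned output. SAP 5.2.1 and 6.1.1.2.1 plan differences only for Tier 1 and Tier 2 terms, so the differences in the first table illustrate the mechanism. SOC and PT rows would reveal an injection-site excess, and on the even-split assumption only a total below 3% in Arm D escapes a Tier 2 row. What survives is narrower: the participant-level totals cannot be corrected from those rows.

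The separation by side is not complete. SAP 3.1.1.1 says local reactions are reported in the e-diary and/or the CRF and combines sources, so right-deltoid reactions entered on the CRF within Days 1 to 7 may feed the reactogenicity tables. Protocol 8.3.4 sends missed-diary events to the CRF without saying that they are AEs.

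Two further inferences go too far. A cross-cohort summary, in which QIV is given in the right deltoid in Arm G, would mix the two recording routes; but SAP 5.2 makes such summaries optional, and no comparison of Arm G with B or D is planned. And one cannot say that no such summary exists anywhere. SAP 3.3 places all safety endpoints in 3.1.1, but that concerns endpoints rather than every table, some text is redacted, and the safety review plan is not available. The claim is limited to the visible SAP.

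**Conclusion.** The concern holds in a limited, conditional form. If QIV-site reactions are reported as AEs more often than saline-site reactions, the any-AE, related-AE and severe-AE rows by arm will look more favourable for the combination with all other AE rates equal, and the visible SAP lists no summary that shows how much of the gap this explains.

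The size is unknown. Under the assumed rates and independence it lies between 0 and -6.65 points in Cohort 2 (-7.0 with no overlap). It shrinks as left-arm reporters overlap with other AE reporters, and it changes sign if saline-site reports are the more frequent. Left-arm events have no diary prompt, and Protocol 8.4 asks for nonleading questioning about AEs, so capture may be at the low end. The related-AE and severe-AE rows also depend on investigators' causality and intensity grading, for which there is no basis for a figure.

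No hypothesis, decision rule or sample size is affected. This is a cheap improvement to a descriptive analysis.

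**What to change.** Keep the all-inclusive AE table as the main analysis. In SAP 6.1.1.2.2, prespecify before unblinding supplementary summaries by arm of any AE, related AEs and severe AEs that exclude solicited-type injection-site reactions (pain, redness, swelling) from both deltoids, using a list of terms fixed in advance. Excluding both sides treats the arms alike and needs no record of injection side, which matters because the documents do not show a laterality field on the AE CRF. The Tier 2 rows need no second version, since the other PT rows do not change.

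The cost is a few lines of SAP text, a term list and the extra summary rows or tables. Data collection does not change. The downside is that the supplementary version drops genuine events of the Arm B and D regimens, so it must stay supplementary and be shown next to the main table.
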